## 6.1 Magtrace injection protocol

Magtrace will be injected by the operating surgeon on day of surgery. This injection will occur prior to surgery, on the admitting ward with massage of the area. If the patient arrives in the theatre suite before being seen by a surgeon, the injection will be given by the surgeon prior to general anaesthetic.

Prior to injection, the surgeon giving the injection must check the pre-operative mammograms and Magseed position. The Magtrace injection should be injected 2cm deep in the breast to avoid staining of the skin, and at a distance to the Magseed. This is to ensure that the Magseed signal is not confused with the Magtrace injection site.

Some examples are given in the Figure below;

# 7. Assessment of Efficacy

# 7.1 Primary Efficacy Parameters

The Primary Endpoint

Cost effectiveness of Magtrace® compared to Technetium in the identification of sentinel nodes in breast cancer.

# 7.2 Secondary Efficacy Parameters

The Secondary Endpoint

- Patient time spent in hospital and in transit in total over pre-operative and perioperative journey
- Patient anxiety on day of surgery as measured using State trait anxiety questionnaire STAI-Y given on ward on morning of surgery.
- Number and length of patient hospital visits comparing preoperative visits
   (clinic visits, preoperative assessment, tracer injection visits, ward visits and
   operative visits).
- Safety of Magtrace® and efficacy adverse events relatable to tracers, number of nodes removed, number of nodes containing tracer, % of patients with detectable tracer in the axillary sentinel nodes, can surgeons differentiate Magtrace® and Magseed signal®.
- Cost per episode and for total care.
- Surgical start time, days of week of operating, and delays to getting patient to theatre. Delays will be recorded by asking the theatre team directly preoperatively whether they had to wait for the patient to arrive, and what the reason was, and also whether the list had to be rescheduled/ moved to accommodate a delay.
- To map the current pathways of patient care.
- Evaluation of the key aspects of care pathways important to patients and healthcare professionals in the management of breast cancer.
- Preferences/overall satisfaction with care package for Magtrace vs.
   Technetium, from the perspective of patients and healthcare providers.

#### 8. Source Data

- Medical records:
- Histopathology reports;
- Data capture worksheets All documents will be stored safely in confidential conditions. On all study-specific documents, other than the signed consent, the participant will be referred to by the study participant number/code, not by name.

## 9. Assessment of Safety

## 9.1 Specification, Timing and Recording of Safety Parameters.

All Serious Adverse Events (SAEs) for participants undergoing randomised treatment will be recorded for as long as the participants is on the trial. . All SAEs should be reported immediately to the Sponsor and where appropriate the regulatory authorities following the Trust SOPs. The immediate reports should be followed promptly by detailed, written reports. The immediate and follow-up reports should identify subjects by unique code numbers assigned to the trial subjects' names, personal identification numbers, and/or addresses.

SAEs are defined as any untoward medical occurrence that:

- Results in death,
- Is life-threatening\*
- Requires inpatient hospitalization or prolongation of existing hospitalization
- Results in persistent or significant disability/incapacity, or
- Is a congenital anomaly/birth defect
- Is otherwise considered medically significant by the investigator

This includes device deficiencies that might have led to a serious adverse event if a) suitable action had not been taken or b) intervention had not been made or c) if circumstances had been less fortunate. These are handled under the SAE reporting system.

A planned hospitalization for pre-existing condition, or a procedure required by the Clinical Investigation Plan, without a serious deterioration in health, is not considered to be a serious adverse event.

All SAEs and SARs will be reported immediately to the Chief Investigator of the Study, [name], and the Research Office at [contact].

The following common post-operative complications will be recorded as Adverse Events but not serious adverse events as they are unlikely to be related to the device itself but can cause rehospitalisation or require further surgery.

- Bleeding requiring hospitalisation, transfusion or further surgery;
- Seroma formation often requiring drainage in the outpatient clinic;
- Skin necrosis requiring debridement.

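### Section 9.1 declares listed complications non-serious because they are presumed unrelated to the device, although some of them meet the section's own outcome-based SAE definition

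*Protocol*

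**What the plan says.** All of the text at issue is in Protocol Section 9.1, apart from two short headings that follow it.

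- **Definition.** It opens "SAEs are defined as any untoward medical occurrence that" and lists outcomes. Among them are "Requires inpatient hospitalization or prolongation of existing hospitalization" and the open criterion "Is otherwise considered medically significant by the investigator". Death and threat to life are also listed. Cause is not mentioned.
- **General exception.** One situation is taken out of the definition: "A planned hospitalization for pre-existing condition, or a procedure required by the Clinical Investigation Plan, without a serious deterioration in health".
- **Consequence of SAE status.** Two sentences require immediate reporting of every SAE, one to the sponsor and one to the Chief Investigator and the research office.
- **Carve-out.** Named post-operative complications "will be recorded as Adverse Events but not serious adverse events as they are unlikely to be related to the device itself", and the sentence continues "but can cause rehospitalisation or require further surgery". The list is "Bleeding requiring hospitalisation, transfusion or further surgery", then "Seroma formation often requiring drainage in the outpatient clinic", then skin necrosis that needs debridement.

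Under the heading Adverse Events requiring reporting, the protocol names two items only: allergy to the Magtrace injection and a Magseed left in the breast. Under Safety Oversight, the Trial Steering Committee (TSC) is to consider both serious and other adverse events.

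**The concern.** Seriousness and relatedness are separate judgements. The definition in Section 9.1 keeps them separate, since an event is serious because of what happened to the patient, whatever the cause. The carve-out merges them by taking events out of the serious class on a presumption about cause, made in advance and for whole categories.

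Two things are at stake. First, an event that qualifies under the definition would be counted as non-serious, so a reader of the SAE count would be given a number that does not match the definition printed beside it. Second, immediate notification of the sponsor depends on SAE status, so a listed event that qualifies would not trigger it. The carve-out has no proviso for fatal or life-threatening cases.

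**Working it through.** No figure in the protocol is in dispute, so the check sets the rules of Section 9.1 side by side.

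**Step 1: does the definition depend on cause?** No. It covers any untoward occurrence with one of the listed outcomes.

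**Step 2: does the general exception cover the listed complications?** No. It is limited to planned admission for an existing condition and to procedures that the plan requires, without serious deterioration. A post-operative bleed that brings a patient back to hospital is neither.

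**Step 3: compare each listed item with the definition.**

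| Listed complication | Meets the SAE definition? | Class under the carve-out |
|---|---|---|
| Bleeding with hospitalisation | Always, by its own description | Not serious |
| Bleeding with transfusion or further surgery only | If it leads to admission, a longer stay, threat to life or a judgement of medical significance | Not serious |
| Seroma | Not when simply drained in the outpatient clinic; otherwise on the same conditions | Not serious |
| Skin necrosis with debridement | On the same conditions | Not serious |

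The first row conflicts on its face. The other three conflict only in the cases that satisfy a criterion.

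**Step 4: does anything return qualifying cases to SAE status?** No. The carve-out contains no such clause. The same sentence accepts that these complications can lead to readmission or another operation, so serious outcomes were foreseen and still classed as non-serious.

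**Step 5: does the stated reason apply to both arms?** SAE recording covers all participants undergoing randomised treatment. The reason refers to the device without saying which one: Magtrace is given in one arm only, whereas Magseed is placed in both. A presumption about an unnamed device cannot replace an assessment of each event.

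**Step 6: what follows for the count and for reporting?** Let k be the number of listed events that meet the definition. The SAE count under the carve-out is the count under the definition minus k, and those k events receive no immediate report as SAEs. They are also absent from the short list of adverse events requiring reporting. The protocol gives no complication rates, so k cannot be estimated from it.

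**The case against.** The strongest reply is that a general definition followed by a named exception is a workable rule: listed events go on the adverse event form and everything else follows the definition. That is fair as far as it goes. Staff can apply it, and it would be too much to say that they could not. But an exception that can be applied may still be wrong. This one gives a reason about cause for a decision about seriousness, and its result disagrees with the definition above it.

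Several stronger readings are tempting, and the documents do not support them:

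- **That the events are lost or hidden from oversight.** They are recorded as adverse events, and the TSC considers adverse events as well as SAEs. What changes is the label and the prompt report.
- **That every listed complication is an SAE.** Outpatient drainage of a seroma alone is not, and skin necrosis or bleeding without admission is so only on the conditions above.
- **That the SAE count is certain to be wrong.** It is affected only if a qualifying event occurs. Purely as an assumption, if 2% to 5% of the 40 main-study patients had one, the expected number would be 40 × 0.02 = 0.8 to 40 × 0.05 = 2. The chance of none at all would be 0.98^40 = 45% to 0.95^40 = 13%.
- **That these would be most of the trial's SAEs.** No rate is given for any SAE, so there is no basis for a share.
- **That a planned comparison is damaged.** The protocol specifies no SAE table by arm. The safety endpoint in Sections 4.1 and 7.2 concerns tracer-related adverse events, and the primary endpoint is cost-effectiveness.

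It can also be said that trials may spare expected complications from urgent reporting. The protocol could do so, but its present text changes the seriousness class instead.

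**Conclusion.** The point holds as an internal contradiction in Section 9.1. The definition makes an event serious by its outcome, and the carve-out makes some of the same events non-serious by presumed cause. The conflict is unconditional for bleeding that requires hospitalisation and conditional for the other listed events. Each qualifying event would lower the SAE count by one against the protocol's own definition and would bypass immediate reporting to the sponsor, even if it were fatal or life-threatening.

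The conclusion rests on the wording alone and needs no assumed rate. Its numerical size cannot be given, and the rates used for illustration above carry no weight in it. The effect is confined to classification, the SAE count and prompt reporting. It does not reach the primary endpoint or the TSC's access to the events. It is worth correcting because the safety rule is wrong as written and the repair is cheap.

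**What to change.** Reconcile the carve-out with the definition in Section 9.1:

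1. Replace the carve-out so that the listed complications are classified and counted as SAEs whenever they meet the definition, and as adverse events otherwise. Assess relatedness separately for each event, in both arms.
2. If the sponsor wants to spare expected complications from urgent reporting, state this as an exemption from immediate reporting only, and say that it does not cover fatal or life-threatening cases.
3. If that exemption is kept, add a matching exception to the two sentences that require immediate reporting of all SAEs, one to the sponsor and one to the Chief Investigator. Changing the carve-out alone would leave the section contradicting itself in a new place.

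The cost is minor edits to three sentences and a slightly higher SAE count if such events occur. With the exemption in place, extra immediate reports arise only for fatal or life-threatening cases. Without it, each qualifying event would be reported immediately. No treatment, visit or endpoint changes.

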## Adverse Events requiring reporting:

- Allergy to Magtrace® injection
- Magseed® device not resected from breast during cancer surgery.

#### Safety Oversight:

The Trial Steering Committee (TSC) will meet once all patients have completed the study or earlier if considered necessary by the Chief Investigator. They will consider all Serious adverse events and adverse events and the main safety and efficacy outcomes.

#### 10. Statistics

#### 10.1 Sample Size

as above within relevant section.

#### 10.2 Randomisation

Patients will be randomised in blocks of ten as surgical pathways may need to change through the study in response to changing COVID requirements of the hospital. The data would still be valid but the groups would need to be matched in size, hence randomising in small blocks. Block size may be increased by the Chief Investigator if it was clear that the surgical site was fixed for a prolonged period.

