#### Methods:

- 1. Part 1. Cost-implications and efficiency gains from using Magtrace® vs the current standard of care: A time-in-motion study
- Part 2. Managing Breast Cancer: What matters when treating breast cancer? Focus Group and Survey
   Patient and Healthcare provider preferences towards the management of

breast cancer: A Discrete-choice experiment

Trial duration per	8 weeks maximum			
participant:				
Estimated total	14 months			
trial duration:	T THORISTO			
Planned trial sites:	Single Centre – Wythenshawe Hospital			
Total number of	Part 1: 50 (5-10 pilot patients, 20 under Magseed, 20 under			
participants	the current SOC).			
planned:	Part 2: Managing Breast Cancer: What matters? A focus-group, will include 5-10 patients to help design the discrete choice experiment.			
	Managing Breast Cancer: What Matters? Survey. Discreet Choice Experiment will include:			
	150 patients			
	50 healthcare professionals			
Part 1 Main	Part 1 Inclusion:			
inclusion/ exclusion criteria:	Participant is willing and able to give informed			
	consent for participation in the study;			
	Female, aged 18 years or above;			
	Diagnosed with breast cancer (invasive) requiring			
	Magseed® localisation and sentinel node biopsy			

- Willing to allow his or her General Practitioner and consultant, if appropriate, to be notified of participation in the study;
- Undergoing breast conserving surgery with sentinel node biopsy
- Surgeons may only operate on the Magtrace arm of the study if they have completed a minimum of five training cases with Magtrace.

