It will be the responsibility of the research assistants to provide a 'learned' assessment, of what they believe represents a 'typical' pathway at the Nightingale centre. A multidisciplinary team will then assess the validity of this pathway and voice any concerns/objections/potential additions. Once an accurate representation of the existing care pathway has been generated (as agreed by research staff and clinical leads), this will be pilot tested among a group of 10 patients (5 current SOC and 5 Magtrace), in order to ensure that all relevant points of interaction with healthcare staff, and utilisation of health services, are captured, the pathway will be amended as necessary. Using a stopwatch, research staff would have the ability to consent and then actively monitor (shadow around the hospital) a group of ~20 patients in each treatment group (Magtrace® vs. routine care using Technetium nuclear medicine). It is critical prior to recruitment that key covariates and factors likely to influence not only outcomes, but also health economic factors of care are identified. These factors will require consideration before randomisation to Magtrace or routine care, with randomisation recommended to take place using sealed envelopes in blocks of ten. If imbalances in key covariates occur following randomisation, adjustment of health economic outcomes will be performed to mitigate these imbalances using gold-standard two-stage bootstrapping for costeffectiveness analyses.

[figure not shown]
Once data is collected for 20 patients undergoing Magtrace, and 20 patients undergoing routine care, it will be possible to multiply NHS resource utilisation by representative NHS unit costs (staff salaries per minute, radiography, inpatient, nuclear medicine) and determine the array of health economic outcomes listed above. The result will be a health-economic comparison of Magtrace® over Technetium nuclear medicine (Figure 1). Sensitivity analyses will be performed on this dataset to measure the robustness of the findings to changes in the values of the parameters measured during the TDABC stopwatch exercise. Rather than relying on point-estimates, this will enable the derivation of credible intervals, and determine

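### The surgeon-training rule binds only the Magtrace arm, so surgeon and arm may be confounded; separately, a published block of ten makes about one allocation in six predictable

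*Protocol*

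**What the plan says.** **Surgeons.** The Study Summary lists among the Part 1 inclusion criteria: "Surgeons may only operate on the Magtrace arm of the study if they have completed a minimum of five training cases with Magtrace". No such condition is set for surgeons operating on Technetium patients, and section 5.2 does not carry the rule.

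**Timing.** In section 4.2 consent, confirmation of eligibility, baseline data and randomisation all belong to Study Visit 1. Surgery follows at Study Visit 2.

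**Blocks.** Section 10.2 states: "Patients will be randomised in blocks of ten as surgical pathways may need to change through the study". Its reason is that "the groups would need to be matched in size, hence randomising in small blocks", and it then gives the power to resize: "Block size may be increased by the Chief Investigator if it was clear that the surgical site was fixed for a prolonged period". The Part 1 design text in section 4.2 describes "randomisation recommended to take place using sealed envelopes in blocks of ten".

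**Covariates.** The same text asks for key covariates to be identified in advance: "These factors will require consideration before randomisation to Magtrace or routine care". It promises adjustment if they turn out unbalanced. It does not name surgeon as one of them.

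**People.** Section 5.1 has a consultant breast surgeon or research nurse, authorised by the Chief Investigator, take consent. Section 4.2 has research staff consent patients and then follow them through the hospital with a stopwatch. Section 6.1 has the operating surgeon inject Magtrace.

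**The concern.** The primary comparison is a time-driven costing, in which staff minutes and grades are turned into money. Operating time plausibly depends on who operates. A rule that restricts surgeons in one arm only can make allocation decide the surgeon: an untrained surgeon's patient allocated to Magtrace cannot be operated on by that surgeon, while the same patient allocated to Technetium can. Randomisation cannot balance a difference that arises after it and because of it. Any difference between the two groups of surgeons would then be read as an effect of the tracer on cost.

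The second issue is foreseeability. The trial is open, at one site, and has one block size printed in the protocol. The people who seek consent also see which tracer earlier patients received. Someone who keeps count can tell when one arm's places in a block are used up. Knowing the next arm could influence whom to approach or when to enrol them, and so bias the case mix. The results from 40 patients are to be extrapolated to annual caseload and return on investment for the Trust, so a selection or surgeon effect would carry through.

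**Working it through.** **A. Surgeon and arm**

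The steps in order are: randomisation at Visit 1; surgery at Visit 2; the five-case rule applied to Magtrace operations only; no stratification by surgeon stated. The documents do not say how many operating surgeons lack the training, or what happens when a patient of such a surgeon is allocated to Magtrace. The imbalance therefore cannot be computed from them.

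As an illustration, assume that a share *s* of patients would be under untrained surgeons, and that those allocated to Magtrace are moved to trained surgeons. With 20 per arm, untrained surgeons operate on 0 Magtrace patients and 20 × *s* Technetium patients:

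| Assumed *s* | Magtrace, of 20 | Technetium, of 20 |
|---|---|---|
| 0% | 0 | 0 |
| 10% | 0 | 2 |
| 25% | 0 | 5 |
| 50% | 0 | 10 |

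Wherever *s* is above zero, some surgeons appear in one arm only. For them there is no Magtrace patient to compare with, so adjustment has to rest on an assumption and not on the data.

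**B. Foreseeable allocations**

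Inputs: block size 10 (sections 4.2 and 10.2); 20 patients per arm ("Once data is collected for 20 patients undergoing Magtrace, and 20 patients undergoing routine care"). The protocol gives no foreseeability figure to reproduce. As a consistency check, 40 / 10 = 4 complete blocks, and 5:5 in each gives 20 and 20.

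Assumptions: 1:1 permuted blocks, block size known, every past allocation in the block known.

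1. Expected allocations that are certain in advance, for a block of 2*m*: 2*m* / (*m* + 1). With *m* = 5: 10 / 6 = 1.67 per block, or 16.7%. Over four blocks: 4 × 1.67 = 6.7 of 40 patients.
2. Expected share guessed correctly by always naming the arm with more places left: [*m* + (2^(2*m*) / C(2*m*, *m*) − 1) / 2] / (2*m*). With *m* = 5: [5 + (1024 / 252 − 1) / 2] / 10 = (5 + 1.532) / 10 = 65.3%, or 26.1 of 40, against 50% by chance.

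An exact recursion over all block sequences gave the same values. The same calculation for other block sizes:

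| Block size | Certain in advance | Of 40 | Guessed correctly |
|---|---|---|---|
| 4 | 33.3% | 13.3 | 70.8% |
| 10 | 16.7% | 6.7 | 65.3% |
| 20 | 9.1% | 3.6 | 61.7% |
| 40 | 4.8% | 1.9 | 58.7% |

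The only change that section 10.2 permits, an increase, moves down this table and lowers foreseeability.

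**The case against.** **All surgeons may be trained.** Section 3.2 describes both tracers as standard of care, used according to availability, and section 3 describes Magtrace as already in use at the site. Nothing says that any study surgeon falls short of five cases, or that randomisation reassigns anyone. This stands as a limit on size: the effect may be nil. It does not remove the one-sided rule, which needs stating only if some surgeons might not meet it.

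**Adjustment and sensitivity analyses are planned.** True, and this softens the point. But surgeon is not named, and adjustment cannot cleanly separate surgeon from tracer where some surgeons treat only controls.

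**Start time, weekday and delays are outcomes.** This stands. Technetium logistics are expected to shift them, so differences there are not in themselves evidence of a surgeon effect.

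**Envelopes are sealed, and eligibility is listed before randomisation.** Sealing stops someone reading the next envelope. It does not stop someone counting the last ones.

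**Details of sequence generation may sit elsewhere.** This stands as to silence: not naming who holds the sequence is no error in itself. The point rests on what the protocol does fix, namely the disclosed block size and the investigator's control of it.

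A reader might infer more than the text supports in three ways:
- That the power to resize makes allocation foreseeable. It allows only larger blocks, which reduces foreseeability.
- That a pathway change in mid-block would leave the arms badly unequal. If the change came exactly halfway through a block, the first five patients would all be in one arm with probability only 2 / 252 = 0.8%.
- That the analysis disregards the blocks. The protocol does not name block or pathway period, but it allows general adjustment, and a SAP may say more.

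**Conclusion.** The point holds in two separate parts, and the rules should be changed.

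First, the five-case rule applies to one arm, with no stated stratification by surgeon. Surgeon and arm are confounded if any operating surgeon is untrained. The size is unknown and nil if all are trained. A reader might want to put a sum in pounds on this, but the documents give no share of untrained surgeons, no difference in operating time, no cost per minute and no direction, so no figure is supported.

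Second, about one allocation in six is certain in advance and 65% can be guessed, provided the recruiting team knows the block size and tracks past allocations. The disclosed block size and the open, single-site setting make that realistic; the documents do not show that anyone would act on it. The fault in the resizing clause is one of control: a design parameter can be changed during an open trial by an investigator close to recruitment.

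**What to change.** 1. State the five-case rule in the body of the protocol as a check before randomisation that applies to both arms: randomise only patients already listed to a surgeon who meets it. Record the operating surgeon for every patient.
2. Replace the fixed block of ten, and the Chief Investigator's power to enlarge it, with a sequence of varying block sizes not disclosed in the protocol. The statistician, or another person independent of recruitment, should prepare it in advance and hold it.

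The cost is protocol wording and a new set of envelopes. Patients of any untrained surgeon would not be recruited; if there are none, the first change costs nothing. With varying blocks the last one may be incomplete, so the arms may end slightly unequal and not exactly 20 and 20.
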